1.4 BENEFIT - RISK ASSESSMENT

Preclinical profiles of BI 655130 (SPESOLIMAB) and clinical data from healthy volunteers trials suggest that BI 655130 (SPESOLIMAB) is safe, tolerable and may address an unmet medical need in UC patients by a dual anti-inflammatory and anti-fibrotic mechanism of action, cf. [Section 1.3](#) and the IB [\[c03320877\]](#).

Results of the PoC trial 1368-0011 in acute GPP demonstrate that BI655130 (SPESOLIMAB) treatment rapidly clears pustules, the primary lesions in GPP, a disease closely linked to loss-of-function mutations in the natural IL36R antagonist. A different pustular inflammatory epithelial disease is PPP, which does not show the clear genetic association to the IL36 signalling pathway as GPP. Although the small pilot study of BI655130 (SPESOLIMAB) in 59 patients with this disease (1368.15) failed to achieve the primary endpoint, a subgroup analysis has shown a strong dose dependent effect on pustule severity, the primary and most burdensome lesion of this disease. These data indicate that BI655130 (SPESOLIMAB) indeed inhibits IL36 in human disease and thus has the potential to also treat other neutrophil granulocyte related inflammatory epithelial diseases such as IBD. The most recent and more detailed information is available in section 6 of the current IB [\[c03320877\]](#).

No relevant animal species is available for toxicology testing of the highly human specific antibody BI 655130 (SPESOLIMAB). However, preclinical toxicology studies with a mouse surrogate antibody have demonstrated the safety of chronic IL-36R inhibition in mice (IB [\[c03320877\] Section 5.2.1](#)).

A total of more than 212 subjects have been exposed to single or multiple i.v. doses of BI 655130 (SPESOLIMAB) as of September 2018 (see IB). BI 655130 (SPESOLIMAB) was safe and well tolerated in four healthy volunteers trials evaluating the i.v. and s.c. formulation (for details cf. [Section 1.1](#) and IB [c03320877](#)).

Moreover, two trials exploring efficacy and safety of single (1368-0011) or multiple (1368-0015) doses of BI655130 (SPESOLIMAB) in patients with Generalized Pustular Psoriasis (GPP, n=7) or Palmoplantar Pustulosis (PPP; n=59) demonstrated the favourable safety profile of BI655130 (SPESOLIMAB) in these severe inflammatory skin diseases. Finally, two (1368 - 0004, 1368-0010) clinical trials exploring efficacy and safety of BI655130 (SPESOLIMAB) in patients with Ulcerative Colitis (UC; target n=10 and 30) are currently ongoing and have not yet indicated a BI655130 (SPESOLIMAB) related safety concern.

Although no direct benefit for individual patients can be assumed, based on the PoC achieved in GPP and the strong preclinical rationale, there is a reasonable chance that BI 655130 (SPESOLIMAB) may not only alleviate signs and symptoms of active ulcerative colitis but even directly promote mucosal and histological healing, which is associated with improved clinical outcomes (reductions in immunosuppressive treatments, hospitalizations, colectomy and colorectal cancer [\[R16-0572\]](#)). Participation in this study may thus help to generate future benefit for larger groups of patients with UC, if BI 655130 (SPESOLIMAB) proves to be successful in treating this disease.

The outcome-guided open label treatment with active drug will maximize the patient's chance for individual benefit. Patients not benefitting from up to 24 weeks of BI 655130 (SPESOLIMAB) induction treatment will discontinue the trial and switch to individualized commercial treatment at the investigator's discretion, which will limit the duration of BI 655130 (SPESOLIMAB) exposure in patients not individually benefitting from such treatment. In contrast, patients achieving a clinical response or remission on induction or re-induction treatment, and thus benefitting individually from BI 655130 (SPESOLIMAB), will have the option to receive long-term treatment to maintain their treatment outcome.

There are no identified or potential risks for-BI655130 (SPESOLIMAB), based on the toxicology programme or any clinical trials conducted for this product to date (see also [Section 1.1](#)). No other IL-36 receptor antagonist is currently approved, providing information on identified risks in molecules of this class.

The risks shown in the table below are hypothetical in nature; these are derived from general safety considerations of immunomodulatory drugs.

Proprietary confidential information © 2022 Boehringer Ingelheim International GmbH or one or more of its affiliated companies

In order to protect the patient's safety during conduct of this trial, an independent Data Monitoring Committee has been established for the periodic review of clinical trial safety data.

Table 1.4:1 Benefit – Risk Assessment

Hypothetical risks of clinical relevance for this trial	Summary of data, rationale for the risk	Mitigation strategy
Investigational Medicinal Product		
Drug-induced liver injury (DILI)	Rare but severe event, thus under constant surveillance by sponsors and regulators.	Timely detection, evaluation, and follow-up of laboratory alterations in selected liver laboratory parameters to ensure patients' safety. See also Section 5.2.6 , adverse events of special interest
Systemic hypersensitivity reaction	After administration of any biologic agent or protein, there is a possibility of occurrence of adverse immune reactions which can be local (e.g redness, pruritus, and or swelling at the injection site) or systemic (e.g. anaphylactic reactions).	Patients with a history of allergy/ hypersensitivity to the systemically administered trial medication agent or its excipients are excluded from the trial. In case of systemic hypersensitivity reactions including anaphylactic reaction emerging during or after administration of trial medication, the investigator should consider in accordance with severity of the reaction and local standard of care to interrupt and treat the condition. Systemic hypersensitivity reaction is defined as AESI. It is subject to close monitoring and investigators are requested assess these conditions using the criteria discussed in the statement paper from Sampson HA [R11-4890].

Table 1.4:1

Benefit – Risk Assessment (cont.)

Investigational Medicinal Product		
Infections	
Inhibition of the immune response with an immune-modulating biologic may increase the risk of infections.
 
A recent characterization of individuals with homozygous IL36R KO mutations revealed that normal immune function was broadly preserved suggesting that IL36 signaling pathway inhibition does not compromise host defences [R11-4890].
	
Screening procedures for infections are established for this trial. Patients with any relevant chronic or acute infections including human immunodeficiency virus (HIV), viral hepatitis or tuberculosis are excluded from the trial. Treatment of infections should be initiated promptly according to standards of care.
 
Severe infections and opportunistic infections are considered AESI for this trial. These conditions and serious infections are subject to close monitoring.

Malignancies	
Inhibition of the immune response with an immune-modulating biologic may increase the risk of a decreased immune defense against malignancies
 
A recent characterization of individuals with homozygous IL36R KO mutations revealed that normal immune function was broadly preserved suggesting that IL36 signaling pathway inhibition does not compromise host defences R17-3632
	
Patients with a recent history of malignancy will be excluded from participation in this trial.
 
In case of occurrence of malignant neoplasm other than appropriately treated basal cell carcinoma or squamous cell carcinoma of the skin or in situ carcinoma of uterine cervix, the investigator should discontinue treatment with BI655130 (SPESOLIMAB).
 
Diagnostics and treatment have to be initiated according to local standard of care.
 
Malignancies represent always serious adverse events and are subject to close monitoring.

Table 1.4:1

Benefit – Risk Assessment (cont.)

Trial procedures		
Blood Sampling	
As with all blood sampling, there is a risk of mild pain, local irritation, or bruising (a black or blue mark) at the puncture site. Furthermore, there is a small risk of light-headedness and/or fainting. In rare cases, the puncture site can also become infected or nerves may be damaged, inducing long-lasting abnormal sensations (paresthesia), impaired sensation of touch and persistent pain.
 
Frequent blood collection may cause anemia (low red blood cell count), which may create a need for blood transfusions.
	
These risks will be addressed by careful safety monitoring and risk mitigation measures such as
 
(a) close clinical monitoring for AEs;(b) selection of experienced sites and site staff;(c) training.
Colonoscopy or sigmoidoscopy with biopsy	
Can be associated with diarrhea, abdominal pain, perforation, bleeding, effects from anaesthetic medications, and infection
	
These risks will be addressed by careful monitoring and risk mitigation measures such as
 
(a) close clinical monitoring for AEs;(b) selection of sites with experienced site staff;(c) colonoscopy/sigmoidoscopy will be done according to the standard local care procedure including local clinic/hospital consent authorizing this procedure(d) training

Table 1.4:1

Benefit – Risk Assessment (cont.)

Trial procedures		
SARS CoV-2 infection	
Trial conduct and protocol-defined procedures do not impose more risk to trial participants. To address potential risks associated with operational aspects related to the participation in clinical trials in the context of the COVID-19 pandemic, different risk mitigation measures are considered, based on local requirements and development of the pandemic.
	
The investigators will take the totality of information related to each single patient and the local COVID-19 situation into consideration when performing the individual benefit-risk assessment on a case-by-case basis. Considering all aspects, the investigator will decide upon each patient's (continued) participation in the planned trials. BI as the sponsor, where required, will support the investigator in their decision finding. It is acknowledged that the investigator may decide to implement protocol deviations where this protects the safety, wellbeing, and/or is in the best interest of the patient.

Table 1.4:1

Benefit – Risk Assessment (cont.)

Trial procedures		
Peripheral Neuropathy	
Three cases reported by the investigator as Guillain-Barré syndrome (GBS) were received in ongoing clinical trials with spesolimab. A panel of independent neurologists and experts in the study of neuropathies assessed the 3 cases. Only 1 met level 4 diagnostic certainty for the diagnosis of GBS (lowest level on Brighton scale of 1 to 4). In that case, there was a coincident infection with SARS-CoV-2. The other 2 cases were assessed as not GBS. Observed cases showed a heterogenous pattern.
 
As per assessment by the panel of external neurologists the nonspecific symptoms and findings in all three cases may best be referred to as peripheral neuropathy.
	
Timely detection, evaluation, and follow-up of suspected peripheral neuropathies to ensure patients' safety.
 
Use of dedicated questions to elicit neurologic history during screening and exclusion criteria to avoid selection of patients with acute demyelinating neuropathy.
 
Targeted Follow up questions to gather detailed information in case of any event during trial to ensure proper decision making.
 
Trial treatment discontinuation criteria as well as criteria for trial treatment restart are implemented for relevant cases.

Based on the findings in the nonclinical studies conducted to date and in accordance with international regulatory guidelines, the inclusion of Women of Child Bearing Potential (WOCBP) in this study is justified. To minimize the risk of unintentional exposure of an embryo or fetus to the investigational drug, WOCBP must agree to the requirements for the pregnancy testing and contraceptive methods described in [Section 4.2.2.2](#)

The preceding trial 1368-0004 has already been completed; last patient last visit occurred on 24 October 2019.

Proprietary confidential information © 2022 Boehringer Ingelheim International GmbH or one or more of its affiliated companies

The preceding induction trial 1368-0005 was prematurely discontinued on 04 Feb 2020 due to failure to meet expected enrollment goals. An unblinded analysis was conducted including 90 patients who have either completed or discontinued through week 12. At time of trial discontinuation, 8 additional patients were ongoing and therefore not included in the interim analysis. Last patient last visit occurred on 18 May 2020.

The main results the interim analysis of trial 1368-0005, are summarized in the tables and figures below.

Table 1.4:2

Interim Analysis trial 1358-0005 Primary endpoint: Clinical Remission at week 12 (RS, NRI)

	Placebo IV	Spesolimab 300 IV SD	Spesolimab 450 IV q4w	Spesolimab 1200 IV q4w
Subjects N (%)	23 (100%)	22 (100%)	21 (100%)	24 (100%)
Subjects with Remission N (%)	0	0	2 (9.5)	2 (8.3)
95% CI	(0, 14.3)	(0, 14.9)	(2.7, 28.9)	(2.3, 25.8)
Risk Difference vs placebo (95% CI)			9.5 (-6.4, 28.9)	8.3 (-7.2, 25.8)

Table 1.4:3

Interim Analysis trial 1358-0005 Secondary endpoint: Mucosal Healing (Endoscopic Improvement) at week 12 (RS, NRI)

	Placebo IV	Spesolimab 300 IV SD	Spesolimab 450 IV q4w	Spesolimab 1200 IV q4w
Subjects N (%)	23 (100%)	22 (100%)	21 (100%)	24 (100%)
Subjects with Endpoint N (%)	0	0	2 (9.5)	2 (8.3)
95% CI	(0, 14.3)	(0, 14.9)	(2.7, 28.9)	(2.3, 25.8)
Risk Difference vs placebo (95% CI)			9.5 (-6.4, 28.9)	8.3 (-7.2, 25.8)

SD: Single dose; RS: Randomized Set; NRI: No response imputation.

Mucosal healing (endoscopic improvement): defined as modified endoscopic Subscore (mESS) ≤ 1 .

Proprietary confidential information © 2022 Boehringer Ingelheim International GmbH or one or more of its affiliated companies

Table 1.4:4

[figure not shown]
Interim Analysis trial 1358-0005 Secondary endpoint: Clinical Response at week 12 (RS, NRI)

	Placebo IV	Spesolimab 300 IV SD	Spesolimab 450 IV q4w	Spesolimab 1200 IV q4w
Subjects N (%)	23 (100%)	22 (100%)	21 (100%)	24 (100%)
Subjects with Endpoint N (%)	5 (21.7)	2 (9.1)	5 (23.8)	6 (25.0)
95% CI	(9.7, 41.9)	(2.5, 27.8)	(10.6, 45.1)	(12.0, 44.9)
Risk Difference vs placebo (95% CI)		-12.6 (-33.9, 9.6)	2.1 (-22.0, 26.5)	3.3 (-20.7, 26.5)

SD: Single dose; RS: Randomized Set; NRI: No response imputation.

Clinical Response: defined as defined as total MCS reduction ≥ 3 pts. and $\geq 30\%$ from BL; AND RBS drop from baseline by ≥ 1 pt., or absolute RBS ≤ 1 pt

[figure not shown]
Figure 1.4:1 Interim Analysis trial 1368-0005 Further endpoint: Median (with Q1 and Q3) of absolute values in C-Reactive Protein (CRP) over time for patients with baseline values above upper limit of normal (SAF,OC)

SD: Single dose; SAF: Safety Analysis Set, OC: Observed case.

Proprietary confidential information © 2022 Boehringer Ingelheim International GmbH or one or more of its affiliated companies

Figure 1.4:2 Interim Analysis trial 1358-0005 Further endpoint: Median (with Q1 and Q3) of absolute values in faecal calprotectine (FCP) over time for patients with baseline values above upper limit of normal (SAF, OC)

SAF: Safety Analysis Set, OC: Observed case.

In summary, the results of the interim analysis of trial 1368-0005, show:

- No clear efficacy of Spesolimab over placebo on clinical endpoints across studies and UC populations.
- Effect in the most strict endpoints (clinical remission, mucosal healing) in few patients treated with higher doses of Spesolimab (450mg q4w and 1200mg q4w), although sample size is too low to show statistical significance.
- No dose response effect in primary and secondary clinical endpoints and in secondary inflammatory biomarkers.
- Spesolimab was safe and well tolerated with no evidence of previously unrecognized safety risks.

An analysis of all patients randomized in trial 1368-0005 (total of 98 patients) will be conducted after cleaning all data of these patients and subsequent data base lock.

An interim analysis was also conducted on data from patients in trial 1368-0017 who rolled over from trial 1368-0005. At time of this interim analysis, 69 patients rolled-over from trial 1368-0005 to trial 1368-0017; of those, 51 patients who did not achieve clinical response in

Proprietary confidential information © 2022 Boehringer Ingelheim International GmbH or one or more of its affiliated companies

trial 1368-0005 received re-induction treatment of Spesolimab 1200 mg IV q4w and 18 patients who achieved clinical response in study 1368-0005 received maintenance treatment with Spesolimab 300 mg s.c. q12w. The main clinical results for patients who completed 12 weeks re-induction treatment or 12 weeks maintenance treatment in trial 1368-0017 are summarized in the table below by previous treatment in trial 1368-0005:

Table 1.4:5

Interim Analysis trial 1358-0017 Clinical endpoints for patients who completed 12 weeks re-induction treatment (TS-RT, NRI) or 12 weeks maintenance treatment (TS-MT, NRI) in trial 1368-0017 by previous treatment in trial 1368-0005

Data cut-off: 19 Feb 2020	Placebo IV	Spesolimab 300 IV SD	Spesolimab 450 IV q4w	Spesolimab 1200 IV q4w
Rolled-over from 1368-0005 to 1368-0017	16	18	20	15
Treated with re-induction (1200mg IV q4w)	10 (100%)	16 (100%)	14 (100%)	10 (100%)
Clinical remission week 12	0	0	0	0
Endoscopic Improvement week 12	0	0	0	0
Clinical response n (%) week 12	1 (10.0)	2 (12.5)	4 (28.6)	2 (20.0)
Treated in maintenance (300mg sc q12w)	5 (100%)	2 (100%)	6 (100%)*	5 (100%)*
Symptomatic remission week 12	0	1 (50.0)	1 (16.7)	2 (40.0)

TS-RT: Treated Set for Re-induction Treatment; TS-MT: Treated Set for Maintenance Treatment; NRI: No response imputation

Patients randomized to placebo in trial 1368-0005 who rolled-over to trial 1368-0017 and received re-induction treatment in trial 1368-0017, received in total 12 weeks of induction treatment with Spesolimab. Patients randomized to Spesolimab in trial 1368-0005 who rolled-over to trial 1368-0017 and received re-induction treatment in trial 1368-0017, received in total 24 weeks of induction treatment with Spesolimab. None of these patients achieved Clinical remission or Endoscopic improvement at week 12 and only few patients achieved Clinical response. Few patients who rolled-over from trial 1368-0005 to trial 1368-0017 and treated with maintenance treatment achieved Symptomatic remission.

Based on the results of the interim analyses of trials 1368-0005 and 1368-0017, the general benefit-risk assessment for patients currently treated in trial 1368-0017 cannot be evaluated. Therefore for these patients, the benefit-risk should be assessed by the investigator on an individual basis to evaluate patient continuation in the trial.

As recruitment of patients has been completed and no patients are ongoing in the preceding trials 1368-0004 and 1368-0005, no more patients can be enrolled in trial 1368-0017.

Summary of benefit-risk assessment

Due to the lack of mechanism- or compound-related safety signals as well as the antagonistic mode of action of BI 655130 (SPESOLIMAB) it is considered unlikely that UC patients be exposed to any undue risks in this trial. Considering the medical need of the development of an effective and well tolerated drug specifically and directly treating the structural aspects of UC, the benefit of this trial is considered to outweigh the potential risks for individual UC patients participating in this trial.

Based on the results of the above mentioned interim analysis of the preceding induction trial 1368-0005 and of trial 1368-0017, a benefit-risk assessment should be done by the investigator together on an individual basis to evaluate patient continuation in trial 1368-0017.

2. TRIAL OBJECTIVES AND ENDPOINTS

2.1 MAIN OBJECTIVES, PRIMARY AND SECONDARY ENDPOINTS

Table 2.1:1 Definitions of Study Outcomes

Outcome	MCS subscore				Total MCS	Mod. MCS	Partial MCS	Additional Requirements
	RBS	mESS	SFS	PGA				
Clinical remission	0	≤ 1	0 or 1, if drop vs BL ¹ ≥ 1	-		≤ 2		
CS-free remission (in pts on CS at BL)	0	≤ 1	0 or 1, if drop vs BL ¹ ≥ 1	-		≤ 2		CS-free ≥ 12 wk and PMR for ≥ 12 wk
Clinical response	≤ 1 , or drop vs BL ¹ ≥ 1	Not missing	Not missing	Not missing	Drop vs BL ¹ ≥ 3 and $\geq 30\%$			
Partial MCS response	≤ 1 , or drop vs BL ¹ ≥ 1	-	Not missing	Not missing			$\downarrow \geq 2$ vs BL ¹	
Partial MCS remission	≤ 1	-	≤ 1	≤ 1			≤ 2	
Endoscopic remission	-	0	-	-				
Endoscopic improvement	-	≤ 1	-	-				
Complete remission	-	0	-	-				Robarts Histology Index (RHI) ≤ 6
Disease flare (after clinical response/remission, i.e. applicable on maintenance treatment only)	$\uparrow \geq 1$ vs BL ²	≥ 2 , AND $\uparrow \geq 1$ vs BL ²					$\uparrow \geq 2$ vs BL ²	pMCS \uparrow and RBS \uparrow from BL ² , conf. in 2 nd indep. Visit, with mESS \uparrow , and neg. enteric pathogens in stool

¹ BL of preceding induction study (1368-0005 Part 1)

² BL of current maintenance study (1368-0017)

Table 2.1:1 Definitions of Study Outcomes (cont.)

Outcome	Definition
Maintained remission	CR wk1+48, AND PMR at $\geq 75\%$ of intervening visits w/o flare
Durable remission	CR wk48, and PMR w/o flare in preceding 24 wks
Disease worsening	Worsening of clinical status or UC symptoms, in the investigator's opinion, requiring: 1) [during steroid taper] a suspension of tapering, or, a reversion of the steroid daily dose to the preceding daily dose, or, 2) treatment with rescue medication
Treatment Failure	Disease worsening, or a drug-related AE leading to discontinuation of study drug
Rescue Medication	New or dose increase of any non-study drug or surgical intervention for new or persist. symptoms of UC
Histological remission (HR)	Robarts Histology Index (RHI ≤ 6)

All criteria have to be met to qualify for the respective outcome at the same time

- Abbreviations: CR - clinical remission; pCR - partial clinical remission; CS - systemic corticosteroids; RBS – rectal bleeding score; mESS – modified endoscopic subscore; pts. - patients; RHI - Robarts Histology Index; SFS – stool frequency score; PGA – physician's global assessment; PMR - partial MCS remission; MCS – MayoScore; BL – baseline of previous parent induction trial
- Total MCS is calculated as the sum of RBS, mESS, SFS and PGA
- Modified MCS is calculated as the sum of RBS, mESS and SFS
- Partial MCS is calculated as the sum of RBS, SFS and PGA

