3. DESCRIPTION OF DESIGN AND TRIAL POPULATION

3.1 OVERALL TRIAL DESIGN AND PLAN

This open label (OL), 7 year, single group, long-term extension study investigates the long term safety and efficacy of BI 655130 (SPESOLIMAB) in patients with moderate-to-severe ulcerative colitis who have completed treatment in previous BI 655130 (SPESOLIMAB) induction trials 1368-0005 Part I and 1368-0004.

Approximately 160 patients who meet the entry criteria are planned to be included in the trial from previous induction trials 1368-0005 Part I and 1368-0004. The treatment will be open-label. Trial will consist of a screening period lasting up to 7 days, followed by a 336 weeks maintenance treatment period and a 16 weeks safety follow-up period. Patients rolling-over into 1368-0017 trial must complete the 12 weeks treatment period (until EOT visit) in the previous induction trial. Patients will be treated according to their previous trial outcome in a following way:

- Patients who have completed treatment in the previous trials showing a clinical response at week 12 will receive BI 655130 (SPESOLIMAB) s.c. maintenance treatment (300mg q4w s.c.) through week 336 of this extension study ([Flowchart 1](#)).
- Patients who have completed treatment in the previous trials, but did not achieve a clinical response at week 12, will receive BI 655130 (SPESOLIMAB) i.v. re-induction treatment (1200mg q4w i.v. for 12 weeks). Those patients who subsequently reach the clinical response (versus baseline of original induction trial) at week 12 of re-induction period, will be entered into the 336 weeks s.c. maintenance treatment phase ([Flowchart 2](#)); while non-responders will be discontinued from treatment and complete early EOT visit and safety follow-up period.
- Patients ongoing on maintenance treatment when CTP version 05 is approved will be asked to re-consent to the change in treatment frequency. After consent, patients will switch from q12w regimen to q4w regimen. Patients who do not wish to consent to this change will be discontinued from the study.

A schematic overview of trial design is shown in [Figures 3.1:1](#) and [3.1:2](#).

Proprietary confidential information © 2022 Boehringer Ingelheim International GmbH or one or more of its affiliated companies

[figure not shown]
Figure 3.1:1 Trial design for responders and non-responders

RESPONDERS

Figure 3.1:2 Trial design in case of a disease flare

DISEASE FLARE

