A disease flare may occur at any time after achievement of a clinical response during *maintenance s.c. treatment* period and is defined as a re-increase in partial MCS score, and a re-increase in rectal bleeding score, observed during a regular or unscheduled study visit, confirmed in an independent subsequent visit and by sigmoidoscopy, in absence of enteric pathogens in stool (for complete definition see [table 2.1: 1](#)). In case of a suspected disease flare, the site will ask the patient to immediately start entering his Mayo score data into the eDiary until the next scheduled or unscheduled visit, and then continue entering the data as planned (i.e. for 14 days preceding each visit). A patient with a (endoscopically confirmed) flare will receive a single i.v. infusion of 1200mg BI 655130 (SPESOLIMAB) as a flare treatment followed by intensified maintenance dosing with 600mg sc. BI 655130 (SPESOLIMAB) q6w. No further maintenance dose escalation is foreseen in case of repeated flares. An additional unscheduled sigmoidoscopy has to be planned at week 12 after the i.v. infusion to check the patient's response status to disease flare treatment.

Patients who experience a disease flare during steroid tapering should follow the same flare treatment instructions specified above, but may suspend further steroid dose reduction or re-escalate dose once in line with the instructions above.

For details of trial procedures please follow the [Flowchart 3](#) (Patients with Disease Flare).

Patients will be discontinued from treatment if they do not achieve clinical response (compared to baseline of original induction trial) or clinical remission within 12 weeks after the initiation of disease flare treatment, or if they experience more than 1 confirmed flares during the trial.

Allowed concomitantly given immune modulators (AZA, 5MP, MTX; see [table 4.2.2:1](#)) can be discontinued after ≥ 52 weeks of s.c. maintenance treatment in patients with durable clinical remission per the Investigator's judgement.

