10. APPENDICES

10.1 MAYO SCORING SYSTEM FOR THE ASSESSMENT OF ULCERATIVE COLITIS ACTIVITY

The Mayo score (Schroeder et al., N Engl J Med, 1987) is a composite disease activity score consisting of four items or subscores: stool frequency (relative to normal), rectal bleeding, physician's global assessment, and endoscopic appearance. As proposed by FDA draft guidance [[R17-0038](#)], the endoscopic subscore is modified so that a value of 1 does not include friability. The overall range of the Mayo score is 0-12 (higher scores being worse) and each subscore has a range of 0-3 ([Table 10.1: 1](#)). At visits without sigmoidoscopy, a partial Mayo score without endoscopy subscore will be assessed. The overall range of this partial Mayo score is 0-9.

In addition, based on FDA's recommendation [[R17-0038](#)], a modified Mayo score will be assessed, which excludes physician's assessment. The overall range of the modified Mayo score is 0-9.

The scores for stool frequency and rectal bleeding will be calculated as an average based on the last 3 non-missing scores from the 7 days prior to each applicable visit, as collected from the patient diary. If the patient undergoes bowel preparation for colonoscopy on any of the days before a visit, the stool frequency and rectal bleeding subscore for that day(s) should be considered missing. In addition, the stool frequency and rectal bleeding subscore will be considered to be missing both on the day of and the day after the endoscopy.

The endoscopic appearance score will be assessed by both, the investigational site and a central reader, who is independent from the investigator.

Table 10.1: 1

Mayo score (adopted from Schroeder et al, 1987)

Components	Subscore	Severity	Score
CLINICAL RESPONSE (Patient's Symptoms)	Stool Frequency ^a (daily)	Normal number of stools for patient	0
		1 to 2 stools more than normal	1
		3 to 4 stools more than normal	2
		≥5 stools more than normal	3
MODIFIED ENDOSCOPIC RESPONSE (Objective Evidence of Inflammation)	Rectal Bleeding ^b (daily)	No blood seen	0
		Streaks of blood with stool	1
		Obvious blood with stool	2
		Blood alone passes	3
	Physician's Global Assessment ^d	Normal	0
		Mild disease	1
		Moderate disease	2
		Severe disease	3
	Endoscopic Appearance ^c	Normal	0
		Mild disease	1
		Moderate disease	2
		Severe disease	3

a Each patient serves as his or her own control to establish the degree of abnormality of the stool frequency.

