## **6.6 HANDLING OF MISSING DATA AND OUTLIERS**

Section 7.5 of the CTP describes the handling of missing data.

The original results (OR) approach implies the presentation of data exactly as observed (not using time windows and not setting values to missing).

OR analysis will be performed on parameters and endpoints that are either not affected by patients' rescue medication use (e.g. plasma concentration level of spesolimab, rescue medication use itself, or disease flare related endpoints), or, if it is not meaningful to apply any imputation rule for the replacement of missing values.

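### A responder who enters maintenance with an endoscopic subscore of 3 cannot meet the current disease-flare definition, so flare counts based on it can only err low

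*Protocol*

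**What the plan says.** - **Flare.** The row of protocol Table 2.1:1 (Section 2.1) headed "Disease flare (after clinical response/remission, i.e. applicable on maintenance treatment only" asks for a rectal bleeding score (RBS) rise of at least 1, a partial Mayo score (MCS) rise of at least 2, and an mESS of at least 2 that has also risen by at least 1. It adds confirmation at a second visit and a stool test negative for pathogens. The rises are measured from footnote 2, "BL of current maintenance study (1368-0017"). The note under the table says "All criteria have to be met to qualify for the respective outcome".
- **Scale.** Protocol Appendix 10.1: "each subscore has a range of 0-3".
- **Clinical response.** The same table asks for a total MCS drop of at least 3 points and 30% from the parent-trial baseline, with RBS at most 1 or down by at least 1. For mESS it asks only that a value be recorded.
- **Entry to maintenance.** Protocol Section 3.1: "Patients who have completed treatment in the previous trials showing a clinical response at week 12 will receive" s.c. maintenance. Re-induction responders enter by the same criterion.
- **Flare text.** Protocol Section 3.1 says "A disease flare may occur at any time after achievement of a clinical response during" s.c. maintenance, outlines the requirements, and refers to Table 2.1:1 for the complete definition.
- **SAP.** Section 6.6 names "rescue medication use itself, or disease flare related endpoints" among the results analysed exactly as observed. The patient-status table in Section 7 counts patients with a flare or with intake of flare medication. The SAP's own flare definition sits in Section 5.4.6 and Table 9.1.1:1, which are not in the text available for review.

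**The concern.** The rule that lets a patient into maintenance and the rule that declares a flare use the same four subscores but do not fit together at the top of the endoscopic scale. Response can be reached on symptoms alone, with the endoscopic score left at its maximum. Flare then demands a further endoscopic rise that the scale does not allow.

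In a single-arm, descriptive trial, flare frequency is one of the main ways to show whether response lasts. If some patients cannot register a flare, they appear as flare-free whatever happens to them. The same patients also fall outside the flare-based treatment and withdrawal text (protocol Sections 3.1, 3.3.4.1 and 4.2.1), so similar symptomatic worsening is recorded and handled differently depending on baseline endoscopy.

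**Working it through.** The plan gives no flare figure to reproduce. The response percentages used below do follow from their counts (Table 1.4:4: 5/23 = 21.7%, 2/22 = 9.1%, 5/21 = 23.8%, 6/24 = 25.0%).

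**1. The ceiling.** Flare needs mESS ≥ baseline mESS + 1. With baseline 3 this is 4, and the maximum is 3. The baseline is fixed, so a patient who enters at 3, heals to 0 and relapses to 3 does not qualify either.

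**2. An example (RBS / stool frequency / physician's global assessment / mESS).** Parent baseline 2/2/2/3, total 9. Week 12: 1/1/1/3, total 6. The drop is 3 points, 3/9 = 33%, and RBS is 1, so this is a clinical response. Later scores of 3/3/3/3 give a partial MCS rise of 9 − 3 = 6 and an RBS rise of 2, but an mESS rise of 0: not a flare.

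**3. All combinations.** Take every integer combination of the four subscores, keep those a clinical responder can have, and ask whether any later combination meets the flare row.

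| Maintenance-baseline mESS | Responder combinations | Symptom part reachable | Full flare reachable |
|---|---|---|---|
| 0 | 48 | 47 | 47 |
| 1 | 47 | 47 | 47 |
| 2 | 44 | 44 | 44 |
| 3 | 38 | 38 | 0 |

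The result is the same with no entry restriction and with an assumed parent-trial entry of total MCS ≥ 6 and mESS ≥ 2. These are score combinations, not patients.

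**4. Who might be affected (protocol Section 1.4).**
- Parent-trial responders, Table 1.4:4: 5 + 2 + 5 + 6 = 18.
- Patients with mESS ≤ 1, Table 1.4:3: 0 + 0 + 2 + 2 = 4. At least 18 − 4 = 14 responders had mESS 2 or 3.
- Re-induction responders, Table 1.4:5: 1 + 2 + 4 + 2 = 9. On endoscopy the text says "None of these patients achieved Clinical remission or Endoscopic improvement at week 12 and only few patients achieved Clinical response", so all 9 had mESS 2 or 3.
- Together 14 + 9 = 23 of 18 + 9 = 27.
- Maintenance patients by arm in Table 1.4:5 are 5/2/6/5, not 5/2/5/6. If the one unmatched patient had mESS ≤ 1, the count is 22 of 27.

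**5. What the missing split does.** Let k of 27 have mESS 3 and assume a true flare proportion p that does not depend on mESS. The countable proportion is p × (1 − k/27). Both p and k are assumptions.

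| p | k = 0 | k = 5 | k = 9 | k = 14 | k = 23 |
|---|---|---|---|---|---|
| 30% | 30.0% | 24.4% | 20.0% | 14.4% | 4.4% |
| 50% | 50.0% | 40.7% | 33.3% | 24.1% | 7.4% |
| 70% | 70.0% | 57.0% | 46.7% | 33.7% | 10.4% |

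**6. Flare-free outcomes.** Maintained and durable remission in Table 2.1:1 both carry a no-flare condition, so the direction is the same, but the reach is narrow. Maintained remission also needs clinical remission at week 1, hence mESS ≤ 1, which an mESS 3 entrant does not have. Durable remission also needs partial MCS remission (total ≤ 2) over the preceding 24 weeks. If that holds at every visit, a symptom rise of flare size fits only when the baseline partial MCS was 0.

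**The case against.** The strongest reply is that most of the SAP's flare structure does not use the definition. The pre-flare period ends, and the post-flare period begins, at the first flare infusion (SAP Section 6.1). The flare-treatment set contains patients who took a flare dose (Section 6.3), and the subgroups count flare treatments (Section 7.8). A patient without flare treatment is labelled correctly there, and the status table also counts flare medication. This stands. A reader might infer that all these analyses misclassify mESS 3 patients, and the documents do not support that. The effect is indirect: treating without sufficient evidence of a flare is important deviation F1.02 (SAP Table 6.2:1), so the definition governs who is meant to be treated.

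A reader might also see a contradiction with protocol Section 3.1. There is none: that sentence concerns timing and defers to Table 2.1:1.

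Nor can the loss be sized by assuming a share at mESS 3 and rescaling the flare rate of more than 50% quoted in Global Amendment 4. No share is reported. That rate also accompanies the amendment that replaced a nadir-based rule with no required mESS rise, so flares recorded under the previous rule are not subject to the ceiling.

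Other points also stand. The figure of 22 to 23 of 27 combines slightly different patient sets and leaves out entrants from 1368-0004. RBS and stool frequency are averages rather than integers, though the ceiling depends only on mESS. Worsening can still surface as rescue medication or early discontinuation. The primary endpoint (TEAE rate) and secondary endpoint (remission at week 336) do not count flares. None of this lets an mESS 3 entrant meet the flare row.

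**Conclusion.** The point holds for the current Table 2.1:1: a clinical responder who enters maintenance with mESS 3 cannot meet the disease-flare definition, and nothing in the available text gives such a patient another criterion. Any flare count based on it, and any outcome that requires absence of flare, can be wrong only in the direction of too few flares.

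The size cannot be stated. Most interim responders had mESS 2 or 3, but the number at exactly 3 could be anywhere from 0 to about 23 of 27.

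The conclusion rests on reading footnote 2 as the maintenance baseline. If it means trial entry, re-induction patients with mESS 3 at screening are caught as well, even if they improved before maintenance. It also assumes that SAP Section 5.4.6 and Table 9.1.1:1 carry over the protocol's definition, which could not be checked. The matter is worth correcting but does not threaten the primary or secondary result.

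**What to change.** **Protocol.** The sponsor should reconcile the clinical response and flare rows of Table 2.1:1, together with the flare-based treatment and withdrawal text, and state which baseline footnote 2 means. No clinical rule is proposed here.

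**SAP.** After checking Section 5.4.6 and Table 9.1.1:1:
- report the number of SAF-MT patients with maintenance-baseline mESS 3, that is, those unable to meet the flare definition;
- present flare results, including the flare line of the patient-status table, for baseline mESS 2 or less as well as overall;
- tabulate the mESS 3 patients separately, with the number who met the RBS and partial MCS parts of the definition.

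**Cost.** One extra table from data already collected, and a smaller denominator for the restricted flare result. In return, the unknown k above becomes a reported count.
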